5.1. Summary of Study Design

In Specific Aim 1, we will monitor for safety, feasibility, and compliance of a home TTNS program for bladder management. In Specific Aim 2, the efficacy of home TTNS will be compared to baseline Incontinence- Quality of Life questionnaire. A bladder diary will also capture important information such as frequency and volume of catheterization, incontinence episodes, and other related observations.

6. METHODS AND ASSESSMENTS

- a. Physical exam will be performed per usual care at TIRR, by the attending SCI physicians. Data will be retrieved from the electronic medical record and placed into the data spreadsheet. Missing data will be requested from the attending physician or directly from the patient.
- b. Transcutaneous Tibial Nerve Stimulation (TTNS) will be placed daily by trained research assistants in the clinic to determine if the subject meets I/E criteria. Skin inspection will be performed before and after the trial stimulation session at the electrode sites.
- c. The Bladder diary will be used to collect data use of TTNS with amperage and presence of toe flexion, pain score 0-10, as well as incontinence episodes and volumes. The research assistant will call weekly to capture the written data and monitor progress with the protocol.

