2.2. Primary Objectives

Primary Objective 1: Safety, feasibility, and compliance of TTNS at home.

Primary Objective 2: Overall satisfaction with TTNS based on survey.

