4. TRIAL SCHEDULE

Table 2. Timeline of protocol per subject

Weeks in Study Protocol

| Activities | 0 | W1 | W2 | W3 | W4 |
|--|---|---------|----|----|----|
| Clinic Enrolment: | | | | | |
| Eligibility screen | X | | | | |
| Informed Consent | X | | | | |
| Incontinence Questionnaire (I-QOL) | X | | | | |
| Side effect questionnaire | X | | | | |
| TTNS demonstration | X | | | | |
| Home | | | | | |
| Bladder diary | | □-----□ | | | |
| I-QOL | | | X | | X |
| TTNS | | □-----□ | | | |
| Discontinue bladder medication | | | X | | |
| Side effect questionnaire/ TTNS survey | | | | | X |

5. STUDY DESIGN (Table 2)

Anticipated number of patients to screen: 40

- Anticipated number of patient to enrol: 20
- Anticipated drop out or loss to follow-up: 4

Approximate time to complete study recruitment: 1 year

Expected duration of subject participation: 4 weeks

TTNS protocol: (please refer to protocol HSC-MS-15-0806) electrodes 2 inch by 2 inch will be placed according to anatomic landmarks, with the negative electrode behind the internal malleolus and the positive electrode 10cm superior to the negative electrode, verified with rhythmic flexion of the toes secondary to stimulation of the flexor digitorum and hallicus brevis. The intensity level will be set to the amperage immediately under the threshold for motor contraction. If there is not contraction seen, maximal tolerable intensity will be used. In addition, if the patient perceives pain, the intensity will be lowered until comfortable. Stimulation frequency of 10 Hz and pulse width of 200ms in continuous mode will be used.^{13, 14}

- Information gathered:
 - o Clinical demographics, morbidity, and Neurologic Exam findings from interview with subjects, exam, and EMR review.

- Bladder diary will include:
 - use of TTNS with amperage and presence of toe flexion, and pain score 0-10
 - log of catheterization, volumes
 - log of incontinence episodes
 - Description of other observed changes, including but not limited to: fatigue, vision changes, mental status, bowel program changes, and sexual function changes.
- Information will be tabulated on an Excel spreadsheet on my personal work desktop, password protected. Any paper data (bladder diary) will be de-identified and retained in a locked drawer in the locked office of the PI.

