6.4. Study Visits and Procedures

- *Screening Visits and Procedures*

Screening will be performed in the SCI clinic by the PI and co-I SCI attendings.

Those that meet the I/E criteria will be approached for the study by the PI and co-I attendings. They have until the study period is complete to decide whether they want to participate. However, they will have to return to clinic to have the TTNS trial performed and the directions for home use.

- *Study Visits and Procedures*

Subjects will have their first study visit after their normal clinic visit. Once consented, we will trial TTNS for a response of toe flexion. If they have a response, they will be included in the study. If no response or not tolerating electric stimulation, they will not be included in the study.

Participants will have direction in clinic on the use of the Stambil+, including written, oral, and smartphone images/video if they have access.

The electric stimulation protocol will use stimulation frequency of 10 Hz and pulse width of 200ms in continuous mode for 30 minutes daily, beginning as soon as possible. For sexually active women of child-bearing age, the home use will begin after the results of a pregnancy test are provided. The goal is daily use of TTNS for 4 weeks.

Subjects will be called weekly to capture the information from the bladder diary log and to monitor progress of protocol. They will also be reminded to change electrodes weekly.

- *Final Study Visit:*

Upon completion of the 4-week protocol, subjects will return with the stimulator and the bladder diary.

- *Post Study Follow up and Procedures*

The data will be statistically analysed in the post-study follow up. Subject participation is not required.

- *Discontinuation Visit and Procedures*

If withdrawal occurs, no evaluation will be required for the final study visit, regardless of the withdrawal reason. There are no safety risks in withdrawing from this study at any point.

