9. SAFETY MEASUREMENTS

9.1. Definitions

An adverse event is any unfavourable and unintended sign, symptom, or disease temporally associated with the use of a medical treatment or procedure that may or may not be considered related to the medical treatment or procedure.

The FDA definition of unanticipated adverse device effect will be used, as followed: *An unanticipated adverse device effect* as defined by FDA regulations at 2CFR 812.3(s) – Any serious adverse effect on health or safety or any life-threatening problem or death caused by, or associated with, a device, if that effect, problem, or death was not previously identified in nature, severity, or degree of incidence in the investigational plan or application (including a supplementary plan or application), or any other unanticipated serious problem associated with a device that relates to the rights, safety, or welfare of subjects.

Skin irritation, inflammation, and electrode burn beneath the electrodes are potential adverse events directly related to the use of electric stimulation.

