9.2. Collecting, Recording and Reporting of Adverse Events

The Investigator will be responsible for collecting and reporting adverse events during the UDS. The research assistant and the PI will collect adverse events related to the randomized control trial.

Grading of the severity of the adverse events will be made by the PI, using the Common Terminology Criteria for Adverse Events v4.0 developed by the National Cancer Institute. The relevant “Burn” category is included below.

| DERMATOLOGY/SKIN | | | | | | | Page 1 of 3 |
|------------------|------------|--|---|---|-------------------------------|-------|-------------|
| | | Grade | | | | | |
| Adverse Event | Short Name | 1 | 2 | 3 | 4 | 5 | |
| Burn | Burn | Minimal symptoms; intervention not indicated | Medical intervention; minimal debridement indicated | Moderate to major debridement or reconstruction indicated | Life-threatening consequences | Death | |

REMARK: Burn refers to all burns including radiation, chemical, etc.

Reporting procedures for:

- Deaths and life threatening events
- other SAEs
- Other adverse events

The PI will report problems according to the UTHSC-Houston IRB policy, specifically in the event which in the opinion of the PI is both unexpected and related and places subjects or others at risk of harm.

The PI will report the reportable events to CPHS via iRIS within 7 days, unless the report involves the death of a participant, in which case the report needs to be provided to CPHS within 24 hours.

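### Withdrawn subjects are excused from final evaluation even when they stop for stimulation intolerance, and no visible home item asks about skin, the named direct device harm

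*Combined protocol and SAP*

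**What the plan says.** **Aim and named harm.** Section 2.2 gives "Primary Objective 1: Safety, feasibility, and compliance of TTNS at home". Section 9.1 states: "Skin irritation, inflammation, and electrode burn beneath the electrodes are potential adverse events directly related to the use of electric stimulation". Section 2.4 calls redness under the electrode common, says it usually clears within an hour, and provides a hypoallergenic electrode when it is still there the following day.

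**Stated skin check.** Section 6, item b, concerns the clinic trial of stimulation: "Skin inspection will be performed before and after the trial stimulation session at the electrode sites".

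**Home period.** The diary (section 5) records stimulation use, amperage, toe flexion, pain, catheterization, volumes and incontinence, plus an open field: "Description of other observed changes, including but not limited to: fatigue, vision changes, mental status, bowel program changes, and sexual function changes". On calls, section 6.4 says: "Subjects will be called weekly to capture the information from the bladder diary log and to monitor progress of protocol", and then: "They will also be reminded to change electrodes weekly". Table 2 in section 4 schedules "Side effect questionnaire/ TTNS survey" at week 4; its items are not shown.

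**General safety collection.** Section 9.2 says: "The research assistant and the PI will collect adverse events related to the randomized control trial". It also reproduces a burn grading table. Section 5 gathers morbidity by interview, examination and record review, and section 9.3 plans a quarterly morbidity review centred on urinary tract infection.

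**End of participation.** Section 6.4 describes the final visit only as return of the stimulator and diary. For withdrawals it requires no final-visit evaluation, whatever the reason, on the ground that withdrawing carries no safety risk. Section 3.5 lists intolerance of electric stimulation, intolerable incontinence and non-compliance as possible reasons for stopping.

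**The concern.** The clinic trial, run by trained staff, has a skin check before and after stimulation. The home sessions, run by the subject or a caregiver for up to 28 days, have none stated, and home use is what the study sets out to test. The sharper problem is the withdrawal rule. A subject who stops because stimulation is not tolerated is among the likeliest to have a skin reaction, and the protocol says that no final evaluation is needed. Its reason, that leaving the study is safe, does not bear on whether an injury that prompted the withdrawal gets recorded.

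At stake is the Aim 1 safety conclusion. Section 11.2 hypothesizes that no unusual adverse events will occur. A report of no skin injury means less if nobody was asked about skin at home or on leaving, and with about 20 subjects one or two unrecorded events would change the summary.

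**Working it through.** The plan states no skin event rate and no skin threshold, so there is no figure to reproduce. The check is mainly textual.

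**1. What each route asks, and whether it is stated to reach a withdrawn subject**

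| Route | Skin item visible? | Stated for withdrawals? |
|---|---|---|
| Clinic inspection (6, item b) | Yes | Takes place before home use |
| Diary stimulation items (5) | No; pain is scored | Up to the point of stopping |
| Diary open field (5) | Not among the examples, but the list is open-ended | Up to the point of stopping |
| Weekly calls (6.4) | No | Not stated after stopping |
| Week-4 questionnaire and survey (Table 2) | Items not shown | Not stated |
| Adverse event collection (9.2) | General duty; no timing or method for home sessions | Not suspended |
| Morbidity by interview, examination, records (5) | General | Not excluded |
| Quarterly morbidity review (9.3) | Focus is urinary tract infection | Uses what has been recorded |
| Final visit (6.4) | No | Evaluation expressly waived |

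Skin events can enter the data by several routes. None visible prompts for them during home use, and the one step tied to leaving the study is waived. The burn table grades an event once it is known; it does not find one.

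**2. Outer limits if losses go unassessed**

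Inputs: 20 enrolled and 4 anticipated losses (section 5), so 20 − 4 = 16 completers. Assume no injury among completers and nothing known about the 4. With x injured among the 4, the proportion among all who started is x/20, x = 0 to 4:

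- lowest 0/20 = 0%; highest 4/20 = 20%.

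If the 4 are replaced under section 3.6 so that 20 complete, 24 have started:

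- lowest 0/24 = 0%; highest 4/24 = 16.7%.

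These are limits, not estimates. Section 5 gives the 4 as dropouts or losses of any kind, and not all would stop for intolerance.

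**3. What a zero result shows even with complete recording**

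One-sided 95% upper bound for 0 events in n: 1 − 0.05^(1/n).

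- n = 14: 0.193
- n = 16: 0.171
- n = 20: 0.139

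These bounds follow from sample size alone and do not change with the fix. They require every event to be recorded.

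**4. Sensitivity to capture (assumed values only)**

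Let p be the true proportion of subjects with a skin event and s the share of events recorded. The chance of recording at least one in n = 20 is 1 − (1 − ps)^20.

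| p | s = 1 | s = 0.5 | s = 0.25 |
|---|---|---|---|
| 0.10 | 0.88 | 0.64 | 0.40 |
| 0.05 | 0.64 | 0.40 | 0.22 |

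Neither p nor s comes from the documents, and no value of s is claimed for this trial. The table shows only that incomplete capture would matter at this sample size.

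**The case against.** The best defence is that a skin question would normally sit in papers that are not in the available text: the case report form and diary log (Appendices 2 and 3), the questionnaire and survey, the home instructions, or inpatient protocol HSC-MS-15-0806, to which section 5 refers. Section 1 reports skin irritation as a category considered in that inpatient study, so the team had it in mind. Skin harm is also anticipated in section 2.4 and graded in section 9.2. The device is a class II prescription stimulator, and such units are routinely prescribed for home use. A daily skin line would mostly log passing redness.

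Much of this stands, and it rules out several stronger readings:

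- A reader might infer that home skin injury would go uncollected. The documents do not support that: general routes exist, and the open diary field is wide enough to include skin.
- A reader might infer that the waiver stops adverse event collection. It covers evaluation for the final visit; the section 9.2 duty and diary data already captured remain.
- A reader might take the reference to a randomized trial in section 9.2 as narrowing that duty. It looks like carried-over text, since the same section mentions UDS, which Table 2 does not schedule.
- A reader might say that the hypoallergenic electrode has no trigger. Section 2.4 gives one, redness persisting to the next day; what is not stated is who asks.
- A reader might compare one inspected clinic session per subject with 28 home sessions, 20/(20 + 20 × 28) = 20/580 = 3.4%, and call that the capture rate. It is not: staff are absent from home sessions by design, and reporting does not depend on staff inspection.

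The defence does not dispose of the withdrawal rule. That is a stated instruction, not a silence, and an unseen form with a skin item would not cure it unless the form is completed when a subject leaves.

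**Conclusion.** The point holds as a cheap improvement. Followed as written, section 6.4 can lose device-harm information from the subjects most likely to have it, and for everyone else the visible text leaves home skin events to unprompted reporting.

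The size of any under-recording cannot be derived from the documents. The 0% to 20% range (0% to 17% with replacement) is an outer limit that assumes no injury in completers and no information at all on the 4 anticipated losses. The same limit would apply to any endpoint left unassessed in those 4.

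The part about the diary and calls depends on the unseen forms lacking a skin item; the part about withdrawal rests on stated text. A reader might conclude that the safety result would be invalid. The documents do not support that: no stated threshold or stopping rule is affected, and the pilot remains usable. Confidence is medium because of the unseen forms.

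**What to change.** 1. In section 6.4, replace the waiver with a brief skin and adverse event question by phone at every withdrawal, or a look at the electrode sites if the device is returned in person.
2. At the existing final visit, look at the electrode sites when the device is handed back.
3. Check the diary log, case report form and survey. Unless they already include it, add one electrode-site line to the diary, covering redness still present the next day, so that a positive answer leads to the hypoallergenic electrode in section 2.4. Ask the same question on the weekly calls, next to the electrode-change reminder.
4. Grade any burn with the section 9.2 table.

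The cost is about 4 short phone contacts for the anticipated losses, a brief look at a visit already planned and, if needed, one diary line and one call question. Subjects carry slightly more diary burden, more minor redness will be recorded, and some of those lost will remain unreachable, so the gap narrows but may not close.

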6.2. Randomization and Blinding

- a. Not Applicable.

6.3. Contraception and Pregnancy Testing

For females of childbearing age included in the trial, **sexually active women with male partners will be excluded.**

Females of childbearing age will have to adhere to medically recommended contraception if sexually active, such as condoms and/or birth control pills.

6.4. Study Visits and Procedures

- *Screening Visits and Procedures*

Screening will be performed in the SCI clinic by the PI and co-I SCI attendings.

Those that meet the I/E criteria will be approached for the study by the PI and co-I attendings. They have until the study period is complete to decide whether they want to participate. However, they will have to return to clinic to have the TTNS trial performed and the directions for home use.

- *Study Visits and Procedures*

Subjects will have their first study visit after their normal clinic visit. Once consented, we will trial TTNS for a response of toe flexion. If they have a response, they will be included in the study. If no response or not tolerating electric stimulation, they will not be included in the study.

Participants will have direction in clinic on the use of the Stambil+, including written, oral, and smartphone images/video if they have access.

The electric stimulation protocol will use stimulation frequency of 10 Hz and pulse width of 200ms in continuous mode for 30 minutes daily, beginning as soon as possible. For sexually active women of child-bearing age, the home use will begin after the results of a pregnancy test are provided. The goal is daily use of TTNS for 4 weeks.

Subjects will be called weekly to capture the information from the bladder diary log and to monitor progress of protocol. They will also be reminded to change electrodes weekly.

- *Final Study Visit:*

Upon completion of the 4-week protocol, subjects will return with the stimulator and the bladder diary.

- *Post Study Follow up and Procedures*

The data will be statistically analysed in the post-study follow up. Subject participation is not required.

- *Discontinuation Visit and Procedures*

If withdrawal occurs, no evaluation will be required for the final study visit, regardless of the withdrawal reason. There are no safety risks in withdrawing from this study at any point.

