10. DATA ANALYSIS

10.1. Data Quality Assurance

The PI will be solely responsible for the accuracy of the data. Single data entry will be performed with plans to check 10% of primary variables as a quality control. Single data entry error rates are slightly higher than 0.5% when performed by trained staff and the minimally improved error rate through double data entry is outweighed by substantial cost savings for single data entry.²⁵ Data anomalies will be reviewed by the PI and clarification and/or correction will be performed. Incomplete entries will be reviewed and corrected if information is available.

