11.2. Statistical and Analytical Plans

This pilot study will serve as an earlier-phase developmental function that will enhance the probability of success in a larger subsequent randomization intervention trial.

In Aim 1, for safety, we hypothesize that there will be no unusual adverse events. However, because UTI is directly related to the bladder, we will focus on the occurrence of UTI. Based on literature, the overall rate of UTI in SCI is about 2.5 episodes per patient per year.¹⁸ As a result, we expect to see .2 episodes per patient during the 4-week study period. Based on that, we construct the stopping rules to stop at 20% UTI rate using lower 90% exact Blyth-Still-Casella confidence bounds. If the number of patients with UTI exceed 3 in the first 5 patients, 4 in the first 10 patients, or 5 in the 14 patients, then patient accrual will be paused pending a review by a medical advisory board comprised of SCI experts.

For feasibility and compliance, we will calculate descriptive statistics to determine the dropout rate and percent of adherence to the prescribed regimen as well as program satisfaction. If the dropout rate is less than 25%, and if subjects complete greater than 70% of daily TTNS use in the 4-week period, we will consider the study has high feasibility/adherence. If more than 80% of subjects report that they were satisfied with the program, then we will consider the study has high satisfaction.

In Aim 2, descriptive statistics will be provided for incontinence episodes, catheterization frequency, volumes voided, and anticholinergic-related side effects after the TTNS. The results along the time will be compared to baseline by paired t test, signed t test, or repeated measure methods when appropriate. Since this is an exploratory study and the efficacy of TTNS in this study will be further studied in future larger studies, Bonferroni correction will not be necessary. TTNS satisfaction will be based on the scores of a TTNS survey and descriptive analysis will be provided as well. We will also check the association between these changes from baseline, as well as bladder medication associations.

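### Home TTNS adherence, part of the primary objective, is measured only by self- or caregiver-report, with no planned check against the returned stimulator

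*Combined protocol and SAP*

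**What the plan says.** Section 2.2 makes compliance a primary matter: "Primary Objective 1: Safety, feasibility, and compliance of TTNS at home". Section 6.4 sets the regimen at 30 minutes a day and adds: "The goal is daily use of TTNS for 4 weeks". Section 11.2 gives the success condition: "If the dropout rate is less than 25%, and if subjects complete greater than 70% of daily TTNS use in the 4-week period". If both parts hold, the plan will call feasibility and adherence high.

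Section 6(c) names the source of the usage data: "The Bladder diary will be used to collect data use of TTNS with amperage and presence of toe flexion". The diary contents listed in section 5 agree: "use of TTNS with amperage and presence of toe flexion, and pain score 0-10". Under sections 6(c) and 6.4, staff telephone weekly to collect what is in the diary and to follow progress. The specific aims have the stimulation given at home by the subject or a caregiver.

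At the final visit in section 6.4, "subjects will return with the stimulator and the bladder diary". Neither that section nor section 7.2, which despite its title covers only storage, describes a usage read-out or a reconciliation with the diary. Section 10.1 describes a 10% check of primary variables in the context of data-entry error, and states: "Incomplete entries will be reviewed and corrected if information is available". Section 3.5 lists non-compliance among the possible reasons for stopping the intervention.

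**The concern.** Unsupervised adherence at home is the main unknown that this pilot sets out to measure. The earlier experience that the protocol relies on came from inpatients. The weekly call relays the diary, so it is not a second measurement. The quality check in section 10.1 concerns data entry and cannot show whether a diary entry is true.

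A subject whose real use is below the bar could therefore be counted as adherent, and the plan has no means of noticing. Section 11.2 presents the pilot as preparation for a larger randomized trial. An overstated adherence figure would carry into that trial's assumptions about how much treatment people actually take at home.

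**Working it through.** **Inputs.** One session a day for 4 weeks (section 6.4) gives 7 x 4 = 28 sessions. The bar is strictly more than 70% (section 11.2). The plan derives no figure for the bar and gives no over-reporting rate, so there is no stated result to reproduce. The over-reporting shares below are assumptions.

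**1. The bar in sessions.** 0.70 x 28 = 19.6, so one subject needs at least 20 sessions (20/28 = 71.4%). The plan does not say whether the bar applies per subject or to the group mean. Steps 2 and 3 take it per subject, and step 4 takes it as a mean.

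**2. False entries needed by one subject.** Share of missed days logged as done = (20 - true sessions)/(28 - true sessions).

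| True sessions | True use | Missed days | False entries needed | Share of missed days |
|---|---|---|---|---|
| 18 | 64% | 10 | 2 | 20% |
| 17 | 61% | 11 | 3 | 27% |
| 14 | 50% | 14 | 6 | 43% |

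**3. Chance that one subject's diary shows at least 20 of 28.** Let t be the true daily rate and f the share of missed days logged as done. The reported rate is t + f(1 - t). The chance is the binomial upper tail with 28 days, treated as independent.

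| t | f = 0 | f = 0.20 | f = 0.40 |
|---|---|---|---|
| 0.60 | 15% (rate 0.60) | 44% (rate 0.68) | 79% (rate 0.76) |
| 0.50 | 2% (rate 0.50) | 15% (rate 0.60) | 53% (rate 0.70) |

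**4. Group-mean reading.** The reported mean equals 70% when f = (0.70 - t)/(1 - t), and f must exceed that value to clear the bar:
- t = 0.65: 0.05/0.35 = 14%
- t = 0.60: 0.10/0.40 = 25%
- t = 0.55: 0.15/0.45 = 33%

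**5. The opposite error.** A subject with 22 true sessions (79%) who leaves 3 unrecorded shows 19 of 28 (68%) and fails the bar. A diary can therefore err in either direction.

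**The case against.** The strongest reply is that the plan has some safeguards and that the bias is unproven. Diary data are collected weekly, which limits back-filling at the end. The paper diary is also returned, so it can be compared with what was reported by telephone. Each TTNS entry asks for amperage, toe flexion and a pain score, which is more than a tick box. Section 11.1 enrols 20 rather than 14 to allow for outpatient non-compliance. The analysis is descriptive, in a convenience sample. All of this is true, but none of it is an independent measure of use: the larger enrolment protects numbers, not measurement.

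A reader might infer several stronger things that the documents do not support:

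- **That the error can only inflate adherence.** Real sessions may go unrecorded, so the net direction is unknown.
- **That section 10.1 lets blank days become completed sessions.** Its sentence on incomplete entries sits in a paragraph on data entry and may mean checking against the paper diary. The fair point is that no rule excludes filling gaps from recall.
- **That subjects are driven to conceal missed sessions.** Section 3.5 gives non-compliance as a possible reason for stopping, with no threshold or automatic rule. An incentive is a reasonable inference but is not stated.
- **That a usage log is being ignored.** The documents do not say that the stimulator stores use. The case report form and sample diary are listed as attachments but are not in the text available, so their content could not be checked.
- **That adherence alone decides feasibility.** Dropout must also be below 25%.

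**Conclusion.** The point holds as a limit on measurement. The primary adherence result rests on self- or caregiver-report, and the plan describes no check against the device that comes back at week 4. On the per-subject reading, two or three false entries would carry a subject with 18 or 17 true sessions over the bar. At a true daily rate of 60%, logging one missed day in five as done raises the chance of passing from 15% to 44%. These figures rest on assumed over-reporting shares and on independent days. They show how sensitive the bar is, and are not evidence that over-reporting will happen. This is a worthwhile, inexpensive improvement that bears on what the trial may claim. It does not invalidate the design.

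**What to change.** In sections 6.4 and 11.2:

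1. State whether the stimulator stores use or run time. If it does, read it at the week-4 return, compare it with the diary and with the prescribed 28 x 30 = 840 minutes, and use the device figure for the more-than-70% bar (more than 588 minutes if only total run time is stored). Note that total run time does not show on which days the device was used.
2. If it stores none, report both the result and the feasibility conclusion as self-reported adherence.
3. In either case, count a day with no diary entry for TTNS use as not done, and do not convert it later from recall, whether at the weekly call or during data cleaning. Do not reject a recorded session only because its amperage is missing.

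Item 3 stops later gap-filling; it cannot stop an invented entry. Only a device record could test that, which is why the label in item 2 matters if no such record exists.

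The cost is a counting rule and, where a read-out is possible, a few minutes at a visit already planned. The downside is that some real but unrecorded sessions will not count, so measured adherence may be slightly lower.

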3.5. Withdrawal Criteria

Possible reasons for discontinuation of study intervention:

- Intolerable incontinence after discontinuation of bladder medications
- Intolerant to electric stimulation
- Non-compliance

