3.6. Subject Replacement

Subjects who drop out will be replaced by recruitment from the SCI clinic and asking for informed consent from those who meet the I/E criteria.

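### The more-than-80% satisfaction criterion (Primary Objective 2) has no stated denominator and the available text requires no survey of leavers, so it can be met mainly on completers

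*Combined protocol and SAP*

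**What the plan says.** Section 2.2 makes satisfaction a primary objective: "Primary Objective 2: Overall satisfaction with TTNS based on survey". Section 11.2 attaches a verdict to it. The condition for high satisfaction reads "If more than 80% of subjects report that they were satisfied with the program". The section does not define the analysis set and gives no rule for a missing survey.

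Four other places decide who will be asked:

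- **Table 2 (section 4)** schedules the TTNS survey once, at week 4, among the home activities.
- **Section 6.4**, on discontinuation: "If withdrawal occurs, no evaluation will be required for the final study visit, regardless of the withdrawal reason".
- **Section 3.6**: "Subjects who drop out will be replaced by recruitment from the SCI clinic". No target number is given for replacement.
- **Section 3.5**, headed as withdrawal criteria, introduces its list with "Possible reasons for discontinuation of study intervention". Two of its three items are "Intolerable incontinence after discontinuation of bladder medications" and "Intolerant to electric stimulation". Nothing says whether a subject who stops stimulation stays in the study for the week 4 survey.

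Section 11.2 also has a feasibility and adherence criterion, in a separate sentence: "If the dropout rate is less than 25%, and if subjects complete greater than 70% of daily TTNS use in the 4-week period". Section 5 anticipates 20 enrolled and 4 dropped out or lost.

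**The concern.** Satisfaction is a judgement that only the subject can supply. If those who leave are not asked, the percentage describes those who stayed. Two of the listed reasons for stopping plausibly go with dissatisfaction, so the missing answers may differ from the observed ones. Replacement adds to this, because a leaver without a survey can be succeeded by a new subject who completes one.

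With 16 to 20 surveys, a few unasked leavers can decide which side of 80% the result falls on. At stake is a favourable verdict on a primary objective when the result among all who started home TTNS is unknown. Section 11.2 presents this pilot as groundwork for a larger randomised trial, so the verdict is likely to be carried forward.

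**Working it through.** **Inputs.** Enrolment of 20 and 4 losses (section 5); 14 subjects regarded as sufficient (section 11.1); a satisfaction cut-off strictly above 80% and a dropout limit strictly below 25% (section 11.2). I take all 20 enrolled as starters and assume that the 4 lost give no survey.

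**The plan's own figures.** 20 − 4 = 16 remain, above the 14 called sufficient. Expected dropout is 4/20 = 20%. Inflating 14 for a 20% loss gives 14/0.80 = 17.5, so 18, which 20 covers. The 14 is a convenience number with no formula behind it.

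**Formula.** Let s be the number satisfied among those surveyed, L the leavers not surveyed, and N all starters. The all-starter proportion lies between s/N (no leaver satisfied) and (s + L)/N (every leaver satisfied).

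**Case 1: 20 starters, 4 lost, no replacement (the plan's figures).**

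- Smallest passing count among 16 completers: 0.80 × 16 = 12.8, so 13. 13/16 = 81.3%, which passes.
- All-starter range at that count: 13/20 = 65% to (13 + 4)/20 = 85%.
- Best completer result, 16/16: the guaranteed all-starter value is 16/20 = 80.0%, which is not more than 80%.

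So without leavers' answers, no completer result can establish the criterion for all 20 starters.

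**Case 2: the 4 are replaced and 20 are surveyed (an assumption, since section 3.6 sets no target).** N = 24.

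- Smallest passing count among 20 surveyed: 0.80 × 20 = 16, and more than 16 means 17. 17/20 = 85%, which passes.
- All-starter range: 17/24 = 70.8% to (17 + 4)/24 = 87.5%.
- 19/20 guarantees only 19/24 = 79.2%. 20/20 guarantees 20/24 = 83.3%, so here only a unanimous result is secure.

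**Does the dropout limit protect the verdict?** 4/20 = 20%, or 4/24 = 16.7% if replaced. Both are below 25%, so the limit is met in each case in which satisfaction passes on completers.

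**What an all-starter denominator requires.**

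| Starters | 80% of starters | Satisfied needed |
|---|---|---|
| 20 | 16 | 17 |
| 24 | 19.2 | 20 |

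With 20 starters, 4 leavers and 16/16 satisfied completers, at least one leaver must be reached and must report being satisfied.

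**The case against.** The strongest reply is that this is a small, unpowered pilot with descriptive statistics. Dropout is reported from the same data, so a reader can see the loss. The weekly calls also record use, pain and incontinence up to withdrawal, so leavers' experience is not wholly unknown. That stands, and it limits the consequence. It does not answer the point, because those records do not contain satisfaction and the plan still issues a pass verdict on it.

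Some stronger readings are tempting but not supported:

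- **That section 6.4 waives or forbids a survey of leavers.** The sentence concerns evaluation for the final study visit, which as described consists of returning the stimulator and diary. Table 2 places the survey among home activities. The accurate statement is that the available text is silent on surveying leavers.
- **That only completers will be surveyed.** The case report form and Appendix 1 (study schedule and design) are not in the available text and could provide for an exit survey. A subject who stops stimulation may also remain to week 4.
- **That leavers are dissatisfied, or that the result will be biased by a given amount.** The listed reasons make dissatisfaction plausible. The 4 anticipated losses also include subjects lost to follow-up, whose reasons are unknown. Hence a range is given, not a bias estimate.
- **That the dropout verdict itself changes with the denominator.** At the plan's 4 losses it passes either way. A change would need more losses, with replacement beyond 20, which the documents do not state.

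**Conclusion.** The concern holds as a gap in definition and data collection. Section 11.2 does not fix the satisfaction denominator, and nothing in the available text requires leavers to be asked. At the plan's own 4 losses of 20, a completer result of 81% passes while the all-starter value is known only to lie between 65% and 85%; a perfect completer result guarantees 80.0% and still falls short. If the 4 are replaced up to 20 surveyed, a passing 85% corresponds to 71% to 88% of all starters.

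The first result assumes that all 20 enrolled start home TTNS and that none of the 4 lost is surveyed. The second also assumes the replacement target. The arithmetic does not show that true satisfaction is low, only that the criterion as written cannot tell. Correcting it is a cheap improvement that should be made before leavers' answers become unrecoverable.

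**What to change.** - **Section 6.4:** state that the TTNS survey will be sought from every subject who withdraws or stops stimulation, using the existing weekly-call process.
- **Sections 11.2 and 3.6:** define satisfaction and dropout over all subjects who start home TTNS, including those later replaced.
- **Section 11.2:** report the completer figure beside the all-starter figure. Give the all-starter figure with its range when surveys still missing are counted first as not satisfied, then as satisfied. State the counts needed: 17 of 20 starters, or 20 of 24 if four are replaced.

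It need not go further: showing both figures and the range is enough, and a special label for results that straddle 80% would be a matter of preference.

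The cost is a few sentences in three sections and about four extra calls. Some leavers will be unreachable or will decline, so part of the range may remain, and the reported figure may be less favourable than the completer one. Sample size and treatment are unaffected.
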